7.2 ADHERENCE TO THE CLINICAL INVESTIGATION PLAN

A deviation is defined as an event where the clinical investigator, site personnel, sponsor or sponsor representative did not conduct the clinical study according to the Clinical Investigational Plan (CIP), EC requirements or the Investigator Agreement. The investigator is not allowed to deviate from the CIP, except as specified under emergency circumstances.

In some cases, failure to comply with the CIP may be considered failure to protect the rights, safety and well-being of subjects, since the non-compliance exposes subjects to unreasonable risks. For example, failure to adhere to the inclusion/exclusion criteria: these criteria are specifically defined by the sponsor to exclude subjects for whom the device is not beneficial and the use involves unreasonable risks. This may be considered failure to protect the rights, safety and well-being of the enrolled subject. Similarly, failure to perform safety assessments intended to detect adverse events

Clinical Investigational Plan Template

may be considered failure to protect the rights, safety and well-being of the enrolled subject. Investigators should seek minimization of such risks by adhering to the CIP.

Simultaneously, in the event that adhering to the CIP might expose the subject to unreasonable risks, the investigator is also required to protect the rights, safety and well-being of the subject by intentionally deviating from the requirements of the CIP, so that subjects are not exposed to unreasonable risks.

It is the responsibility of the investigator to provide adequate medical care to a subject enrolled in a study.

Regulations require that the PI maintain accurate, complete, and current records, including documents showing the date of and reason for every deviation from the Clinical Investigational Plan. Relevant information for each deviation will be documented on a Deviation Case Report Form (CRF). The site will submit the CRF to St. Jude Medical.

Regulations require investigators to obtain approval from St. Jude Medical and the EC (as required) before initiating changes in or deviations from the protocol, except when necessary to protect the life or physical well-being of a subject in an emergency. Under emergency circumstances, deviations from the CIP to protect the rights, safety and well-being of human subjects may proceed without prior approval of the sponsor and the EC. Such deviations shall be documented and reported to the sponsor and the EC as soon as possible, but no later than 5 working days.

Prior approval must be requested when the PI anticipates, contemplates, or makes a conscious decision to depart from the CIP, except when unforeseen circumstances are beyond the investigator's control (e.g. a subject who fails to attend a scheduled follow-up visit, a subject is too ill to perform a CIP-required test, etc.). All deviations, including those beyond the investigator's control, must be reported on a deviation CRF.

To obtain approval, the PI may call or email and discuss the potential deviation with St. Jude Medical or designee prior to initiating any changes.

All deviations must be reported to appropriate CA in specified timelines (if appropriate). The Investigator is required to adhere to local regulatory requirements for reporting deviations to EC.

7.3 REPEATED AND SERIOUS NON-COMPLIANCE

In the event of repeated non-compliance or a one-time serious non-compliance, as determined by the sponsor, a Clinical Research Associate or clinical representative will attempt to secure compliance by one or more of the following actions:

- Visiting the investigator
- Contacting the investigator by telephone
- Contacting the investigator in writing
- Retraining of the investigator

If an investigator is found to be repeatedly non-compliant with the signed agreement, the CIP or any other conditions of the clinical study, the sponsor will either secure compliance or, at its sole discretion, terminate the investigator's participation in the clinical study.

8.0 ADVERSE EVENT, ADVERSE DEVICE EFFECT, DEVICE DEFICIENCY

8.1 **DEFINITIONS**

8.1.1 Medical device

Any instrument, apparatus, implement, machine, appliance, implant, software, material or other similar or related article

- Intended by the manufacturer to be used, alone or in combination, for human beings for one or more of the specific purpose(s) of
 - Diagnosis, prevention, monitoring, treatments or alleviation of disease,
 - o Diagnosis, monitoring, treatment, alleviation of, or compensation for, an injury,
 - Investigation, replacement, modification, or support of the anatomy or of a physiological process,
 - Supporting or sustaining life,
 - Control of conception,
 - Disinfection of medical devices and
- Which does not achieve its primary intended action in or on the human body by pharmacological, immunological or metabolic means, but which may be assisted in its intended function by such means

8.1.2 Adverse Event (AE)

Any untoward medical occurrence, unintended disease or injury, or untoward clinical signs (including abnormal laboratory findings) in subjects, users or other persons, whether or not related to the investigational medical device under study.

This definition includes events related to the investigational medical device or the comparator. This definition includes events related to the procedures involved.

8.1.3 Serious Adverse Event (SAE)

An adverse event that led to:

- Death
- A serious deterioration in the health of the subject, that either resulted in:
 - A life-threatening illness or injury OR
 - A permanent impairment to a body structure or a body function OR
 - An in-patient or prolonged hospitalization OR
 - A medical or surgical intervention to prevent life-threatening illness or injury or permanent impairment to a body structure or a body function OR
- Fetal distress, fetal death or a congenital abnormality or birth defect

A planned hospitalization for a pre-existing condition, or a procedure required by the CIP is not considered a serious adverse event.

8.1.4 Adverse Device Effect (ADE)

An adverse event related to the use of an investigational medical device.

This definition includes adverse events resulting from insufficient or inadequate instructions for use, deployment, implantation, installation, or operation, or any malfunction of the investigational medical device.

Clinical Investigational Plan Template

This definition includes any event resulting from the use error or from intentional misuse of the investigational medical device.

8.1.5 Serious Adverse Device Effect (SADE)

Adverse device effect that has resulted in any of the consequences characteristic of a serious adverse event.

8.1.6 Anticipated Serious Adverse Device Effect (ASADE)

A serious adverse device effect which by its nature, incidence, severity or outcome has been previously identified in the risk analysis report.

8.2 PROCEDURE FOR ASSESSING, RECORDING, AND REPORTING ADVERSE EVENTS, DEVICE DEFICIENCIES/COMPLAINTS, ADVERSE DEVICE EFFECTS, SERIOUS ADVERSE EVENTS, AND SERIOUS ADVERSE DEVICE EFFECTS:

Safety surveillance within this study and the safety reporting both performed by the investigator, starts as soon as the subject is enrolled in this study (date of signature of the informed consent). The safety surveillance and the safety reporting will continue until the last investigational visit has been performed, the subject is deceased, the subject/investigator concludes his participation into the study or the subject/investigator withdraws the subject from the study, except as otherwise specified in the CIP.

For the list of anticipated adverse events and adverse device effects please refer to the section 3.3 of this CIP.

Reportable events to sponsor are considered:

- All Serious Adverse Events (whether or not the event is considered device or procedure related)
- All procedure and device-related Adverse Events (whether or not the event is considered serious).

All above events will be reported to the sponsor, as soon as possible, but no later than 72 hours of first learning of the event.

The investigator will report the event to the EC and CA (if applicable) per national and local laws and regulations.

The sponsor will ensure that all events are reported to the relevant authorities as per regulations. Additional information may be requested, when required, in order to support the reporting of AEs to regulatory authorities.

All reportable adverse event data including deaths will be collected throughout the clinical study and will be reported to the sponsor on a dedicated CRF through the Electronic Data Capture (EDC) system.

Records relating to the subject's subsequent medical course must be maintained and submitted (as applicable) to the sponsor until the event has subsided or, in case of permanent impairment, until the event stabilizes and the overall clinical outcome has been ascertained. Adverse events will be monitored until they are adequately resolved. The status of the subject's condition should be documented at each visit.

8.3 SUBJECT DEATH

8.3.1 Procedure for recording and reporting subject death

All subject deaths are to be documented and reported to the sponsor within 72 hours after becoming aware of the event.

Should death occur, the investigator is requested to record death information in the hospital records and immediately document the information on the Death form. By completing the form the sponsor will be notified.

8.4 DEVICE DEFICIENCY /COMPLAINTS

A Device Deficiency is defined as an inadequacy of a medical device with respect to its identity, quality, durability, reliability, safety or performance. Device deficiencies include malfunctions, use errors and inadequate labeling.

All device deficiency/ complaints in St. Jude Medical market-released products must be reported to St. Jude Medical (SJM). The investigator should notify the SJM representative or SJM Product Surveillance Department by emailing the information about a complaint to the following e-mail address: [contact] or calling at: [contact] as soon as possible after becoming aware of a complaint.

9.0 DATA MANAGEMENT

Overall, the sponsor will be responsible for the data handling.

The sponsor and/or its affiliates will be responsible for compiling and submitting all required reports to governmental agencies.

Data will be analyzed by the sponsor and may be transferred to the sponsor's locations outside of Europe and/or any other worldwide regulatory authority in support of a market-approval application.

St. Jude Medical respects and protects personally identifiable information that we collect or maintain. As part of our commitment, St. Jude Medical is certified to the U.S. - European Union Framework and U.S. – Swiss Safe Harbor Framework Agreements regarding human resources and subject clinical trial personal information. The privacy of each subject and confidentiality of his/her information will be preserved in reports and when publishing any data. Confidentiality of data will be observed by all parties involved at all times throughout the clinical study. All data will be secured against unauthorized access.

The Principal Investigator or institution will provide direct access to source data during and after the clinical study for monitoring, audits, EC review and CA inspections. As required, the Principal Investigator or institution will obtain permission for direct access to source documents from the subject, hospital administration and national regulatory authorities before starting the clinical study.

9.1 DATA MANAGEMENT PLAN

A detailed Data Management Plan (DMP) will be established to ensure consistency of the data. This document will include procedures used for data review, database cleaning, and issuing and resolving data queries. If appropriate, the DMP may be updated throughout the study duration. All revisions will be tracked and document controlled.

Clinical Investigational Plan Template

CRF data will be captured in a validated electronic database management system hosted by St. Jude Medical.

Only authorized site personnel will be permitted to enter the CRF data through the electronic data capture (EDC) system deployed by St. Jude Medical. An electronic audit trail will be used to track any subsequent changes of the entered data.

9.2 DOCUMENT AND DATA CONTROL

9.2.1 Traceability of documents and data

The investigator will ensure accuracy, completeness, legibility and timeliness of the data reported to the sponsor on the CRFs and in all required reports.

9.2.2 Recording data

Source documents will be created and maintained by the investigational site team throughout the clinical study.

The data reported on the CRFs will be derived from, and be consistent with, these source documents, and any discrepancies will be explained in writing.

The CRFs will be validated (eCRF) by the authorized site personnel.

10.0 MONITORING

It is the responsibility of St. Jude Medical as the sponsor of the study to ensure the study is conducted, recorded, and reported according to the approved protocol, subsequent amendment(s), applicable regulations, and guidance documents. Monitoring will be conducted according to the St. Jude Medical Clinical Monitoring standard operating procedure.

Prior to beginning the study, St. Jude Medical will contact the investigator or designee to discuss the study and data requirements. A St. Jude Medical monitor will periodically review the subject records and associated source documents.

The investigator shall make subject and study records available to the clinical monitor for monitoring.

11.0 **REGULATORY INSPECTIONS**

The investigator and/or delegate should contact St. Jude Medical immediately upon notification of a governmental agency inspection at the site. A clinical monitor or designee will assist the investigator and/or delegate in preparing for the audit.

An investigator who has authority to grant access will permit authorized governmental agency employees, at reasonable times and in reasonable manner, to enter and inspect any establishment where devices are held (including any establishment where devices are used or where records or results are kept).

An investigator, or any person acting on behalf of such a person with respect to the study, will permit authorized governmental agency employees, at reasonable times and in reasonable manner, to inspect and copy all records relating to the study.

Clinical Investigational Plan Template

An investigator will permit authorized governmental agency employees to inspect and copy records that identify subjects, upon notice that governmental agency has reason to suspect that adequate informed consent was not obtained, or that reports required to be submitted by the investigator, to the sponsor or EC have not been submitted or are incomplete, inaccurate, false or misleading.

12.0 STATISTICAL CONSIDERATIONS

12.1 STATISTICAL DESIGN, HYPOTHESES, METHOD AND ANALYTICAL PROCEDURES

This study has two primary safety hypotheses (1) freedom from device/system-related complications at 12 months and (2) freedom from pressure sensor failure at 12 months. Both hypotheses must be met in order to declare the study successful. Additionally, patient data transmission success at 12 months will be summarized to characterize the primary clinical performance endpoint.

12.1.1 Freedom from Device/System-related Complications at 12 months

The hypothesis is formulated as:

 H_0 : Freedom from device/system-related complications at 12 months ≤ 0.80

H_a: Freedom from device/system-related complications at 12 months > 0.80

where device/system-related complication is defined in Section 4.4.1.

Sample Size

The CHAMPION Clinical Trial observed 98.6% freedom from device/system-related complications (DSCR) at 12 months⁷. The study size of 230 implanted subjects provides at least 85% power to reject the null hypothesis at the significance level of 5% using exact test for a binomial proportion, under the conservative assumption that freedom from device/system-related complications at 12 months is as low as 87%. The sample size was estimated using PASS 13 (NCSS LLC.).

Subject Group

All subjects who are consented and received a sensor implant or undergo the implant procedure but did not receive a sensor implant regardless of study completion status will be included in the analysis.

Analysis

The desired outcome is to reject the null hypothesis. Subjects not experiencing DSRC prior to withdrawal will be treated as not experiencing a DSRC event. The endpoint will be evaluated using the exact test for a binominal proportion. The null hypothesis will be rejected if the 95% lower confidence bound (LCB) is greater than 0.8.

The freedom from device/system-related complications at 12 months will also be reported using the Kaplan-Meier method.

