4.2.1 Number of subjects required to be included in the study

A total of 230 subjects will be implanted in the study (refer to section 12.2 (sample size)). Study enrollment will be closed when a total of 230 subjects are implanted.

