6.5 IMPLANT VISIT

Following completion of informed consent and collection of the baseline visit, subjects will have a sensor implant. All subjects must have complete implant information provided. The implant procedure will be performed according to the User's Manual/Instructions For Use and the hospital standard of care.

Template: 86357 Rev. A

Page 25 of 65

Clinical Investigational Plan Template

Consented subjects who undergo the implant procedure but without a suitable target pulmonary artery branch will not receive the PA Sensor implant and will be withdrawn from the study after being followed for 30 days for safety (unscheduled visit and withdrawal CRF to be completed). In addition, any subject with a failed PA sensor implant due to any other reasons will be followed for 30 days for safety, then withdrawn from the study, and will resume his/her regular standard of care with his/her physician (unscheduled visit and withdrawal CRF to be completed). If an AE occurred during that period of 30 days, an AE CRF needs to be completed.

If a subject was consented to participate in the study and was implanted but does not meet inclusion/exclusion criteria, this is considered a protocol deviation (PD). A PD form needs to be completed and the sponsor must be informed. The EC and Competent Authority (CA) should be notified (if applicable) about any deviations related to the eligibility criteria.

- The following medical information will be collected at this visit
 - Right Heart Catheterization/implant procedure information
 - o Catheter access information
 - Confirmation of target vessel size
 - Initial PA catheter measurement (PA pressures, Cardiac Output (preferably by measured Modified FICK or thermodilution))
 - Implant location
 - o Device and PA catheter measurements (PA Pressures, Heart Rate, Cardiac Output)
 - Device information
 - Sensor serial number

Prior to hospital discharge, subjects will be trained on the home monitoring system and instructed to take pulmonary artery pressure measurements daily. It is recommended that the pressure measurements be taken at the same time in the morning. Subjects will be supplied with a patient implant identification card, a patient system manual, and a helpline phone number.

It is recommended that subjects who are not being treated with chronic anticoagulant therapy be placed on dual antiplatelet therapy for 1 month following the procedure.

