12.1.2 Freedom from Pressure Sensor Failure at 12 Months

The hypothesis is formulated as:

 H_0 : Freedom from pressure sensor failure at 12 months ≤ 0.90

 H_a : Freedom from pressure sensor failure at 12 months > 0.90

where pressure sensor failure is defined in Section 4.4.1.

Template: 86357 Rev. A

Page 36 of 65

Clinical Investigational Plan Template

Sample Size

The CHAMPION Clinical Trial observed 100% freedom from pressure sensor failure at 12 months⁷. The study size of 230 implanted subjects provides at least 85% power to reject the null hypothesis at the significance level of 5% using exact test for a binomial proportion under the conservative assumption that the freedom from pressure sensor failure at 12 months is as low as 95%. The sample size was estimated using PASS 13 (NCSS LLC.).

Subject Group

All subjects who are consented and successfully implanted with a pressure sensor regardless of study completion status will be included in the analyses.

Analysis

The desired outcome is to reject the null hypothesis. Subjects not experiencing pressure sensor failure prior to withdrawal will be treated as not experiencing a pressure sensor failure event. The endpoint will be evaluated using the exact test for a binominal proportion. The null hypothesis will be rejected if the 95% lower confidence bound (LCB) is greater than 0.9.

The freedom from pressure sensor failure at 12 months will also be reported using the Kaplan-Meier method.

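### Both primary safety tests count event-free withdrawals as 12-month successes, so any bias is upward and the stated 5% level is not assured

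*Combined protocol and SAP*

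**What the plan says.** Section 12.1.1 tests whether freedom from device/system-related complications (DSRC) at 12 months exceeds 0.80. Section 12.1.2 tests whether freedom from sensor failure at 12 months exceeds 0.90. Each is decided by a 95% lower bound from an exact binomial test. On subjects who leave early:

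- DSRC: "Subjects not experiencing DSRC prior to withdrawal will be treated as not experiencing a DSRC event".
- Sensor failure: "Subjects not experiencing pressure sensor failure prior to withdrawal will be treated as not experiencing a pressure sensor failure event".

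Section 12.1 adds: "Both hypotheses must be met in order to declare the study successful".

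A time-to-event estimate is planned for both endpoints: "The freedom from device/system-related complications at 12 months will also be reported using the Kaplan-Meier method", and likewise "The freedom from pressure sensor failure at 12 months will also be reported using the Kaplan-Meier method". Neither has a stated confidence bound or a part in the decision.

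The DSRC set also holds subjects who "undergo the implant procedure but did not receive a sensor implant regardless of study completion status". Section 6.5 says that those without a suitable vessel "will not receive the PA Sensor implant and will be withdrawn from the study after being followed for 30 days for safety", and treats other failed implants the same way. Sections 12.8 and 12.9 say only that all available data are used.

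**The concern.** The hypotheses concern a full year, but a subject who leaves event-free at month 2 scores the same as one observed event-free to month 12. An event after withdrawal is unseen and becomes a success; the reverse cannot happen. Compared with complete follow-up, the counted proportion is therefore either right or too high, and dropout makes a safety test easier to pass. Study success rests on these two tests, so their level near the performance goals is what is at stake.

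**Working it through.** **Step 1. Reproduce the design.** Inputs (12.1.1, 12.1.2, Appendix I): N = 230, goals 0.80 and 0.90, alternatives 0.87 and 0.95, one-sided 5%, reject at 195 and 215 or more event-free subjects.

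- DSRC: P(X ≥ 195 | 230, 0.80) = 0.0385; power at 0.87 = 0.8631.
- Sensor: P(X ≥ 215 | 230, 0.90) = 0.0436; power at 0.95 = 0.8840.

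These match Appendix I. One success fewer gives 5.55% and 7.14%, so the cut-offs are right for complete data.

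**Step 2. Add withdrawal.** The documents give no withdrawal rate, withdrawal timing or event timing for these endpoints, so all three are assumptions. Let e be the probability of an event at implant and h a constant hazard afterwards. Freedom at time t, as a fraction of 12 months, is S(t) = (1 − e)·exp(−h·t), with S(1) equal to the goal p0. A share w withdraws at uniform times C, independently of events. Then

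counted freedom = (1 − w)·p0 + w·E[S(C)], where E[S(C)] = (1 − e − p0)/h.

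Type I error is the binomial tail in Step 1 evaluated at the counted freedom.

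- Constant hazard (e = 0), DSRC: h = −ln 0.80 = 0.22314; E[S(C)] = 0.20/0.22314 = 0.8963. At w = 0.10: 0.9 × 0.80 + 0.1 × 0.8963 = 0.8096, tail 7.9%.
- Constant hazard, sensor: h = −ln 0.90 = 0.10536; E[S(C)] = 0.10/0.10536 = 0.9491. At w = 0.10: 0.9 × 0.90 + 0.1 × 0.9491 = 0.9049, tail 7.1%.
- 80% of events at implant, DSRC: e = 0.16; h = −ln(0.80/0.84) = 0.04879; E[S(C)] = 0.04/0.04879 = 0.8198. At w = 0.20: 0.8 × 0.80 + 0.2 × 0.8198 = 0.8040, tail 5.2%.

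Type I error, DSRC / sensor:

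| Withdrawal | Constant hazard | Half of events at implant | 80% at implant | All at implant |
|---|---|---|---|---|
| 0% | 3.85% / 4.36% | 3.85% / 4.36% | 3.85% / 4.36% | 3.85% / 4.36% |
| 5% | 5.6% / 5.6% | 4.7% / 4.9% | 4.2% / 4.6% | 3.85% / 4.36% |
| 10% | 7.9% / 7.1% | 5.6% / 5.6% | 4.5% / 4.8% | 3.85% / 4.36% |
| 20% | 14.9% / 11.0% | 8.0% / 7.1% | 5.2% / 5.3% | 3.85% / 4.36% |

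Withdrawal timing matters too. At 20% with constant hazard, early withdrawal (mean 3 months) gives 25.9% / 16.7% and late withdrawal (mean 9 months) 7.8% / 7.0%.

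**Step 3. Size of the DSRC set.** Section 4.2.1 says "Study enrollment will be closed when a total of 230 subjects are implanted", and failed implants are added, so the set exceeds 230 if any implant fails. With an assumed 1 to 13 failed implants (N = 231 to 243) and uniform withdrawal, DSRC type I error is 7.3–9.9% at 10% and 14.0–18.1% at 20% with constant hazard. With 80% of events at implant it is 4.1–5.7% and 4.8–6.6%.

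**Step 4. From one test to the study.** If both truths sit at their goals and the endpoints are independent, false study success with constant hazard is about 0.079 × 0.071 = 0.6% at 10% withdrawal and 0.149 × 0.110 = 1.6% at 20%. It reaches the per-test rates only when the other endpoint is comfortably met.

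**Step 5. A bound that allows for censoring.** A one-sided 95% log-log Kaplan-Meier lower bound, simulated at N = 230 with constant hazard, 10% and 20% withdrawal and 20,000 trials per setting, had type I error between 4.1% and 4.7% over both endpoints. Power at 0.87 / 0.95 was about 86% at 10% withdrawal and 84% at 20%.

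**The case against.** The strongest reply is that little turns on this in practice. Sections 12.1.1 and 12.1.2 cite 98.6% and 100% freedom in the earlier randomized trial of the device. The tests allow 230 − 195 = 35 complications and 230 − 215 = 15 sensor failures; at 98.6% about 230 × 0.014 = 3.2 complications are expected. Even if 10% withdrew and all were scored as complications, the DSRC test would pass with probability about 97%. That worst-case check does not carry over to the sensor test, which would pass only 4.4% of the time, but at 100% freedom there are no failures to miss. This reply stands as to the likely verdict. It does not restore the stated level near the goals.

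The plan also limits losses. Section 4.6.2 excludes subjects not expected to complete follow-up. Section 6.12 asks for retention efforts and a final visit, and follows an adverse event that caused withdrawal until it resolves or stabilizes. These reduce the bias. Otherwise, events after withdrawal remain unseen.

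A reader might infer more than the documents support:

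- That the 5% level is exceeded. Discreteness leaves some slack, and few withdrawals or events clustered at implant would keep the level at or below 5%.
- That 20% withdrawal is expected. That allowance in Appendix I belongs to the HF hospitalization calculation.
- That event-free deaths inflate the result. Section 6.12 lists death as a withdrawal reason, but those subjects are fully observed for these endpoints.
- That the power claim of 85% or more is wrong. Under the current rule withdrawal only raises the chance of passing, and at 87% / 95% passing is the correct decision.

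**Conclusion.** The point holds in a limited form. In both deciding tests, unobserved time after an event-free withdrawal or loss counts as success. The direction is certain: zero or upward. The one-sided 5% level is therefore not assured. The size is conditional: at N = 230 with uniform withdrawal of 5% to 20%, per-test type I error runs from no inflation (all events at implant) to 14.9% / 11.0% (constant hazard, 20%). No single value, and no break-even withdrawal rate, can be read off the plan. The Kaplan-Meier report would let a reader see a divergence but cannot change the decision. The rule should be corrected because it governs study success, though it is unlikely to alter the conclusion if freedom is close to the cited figures.

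**What to change.** In 12.1.1 and 12.1.2, base the decision on the one-sided 95% lower bound (log-log, Greenwood variance) of the planned 12-month Kaplan-Meier freedom, and specify:

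- Withdrawals and losses are censored at last contact.
- The time point is day 365, with a rule for subjects seen early in the ±30-day visit window.
- Event-free death and, for DSRC, the planned 30-day exit after a failed implant are event-free terminal states, not censoring. The estimate is then 1 minus the cumulative incidence, which equals Kaplan-Meier when there are none; name its variance estimator.
- If no event occurs, the exact bound is used on subjects observed to 12 months or to a terminal state.

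Report the planned exact test alongside. Requiring both bounds to exceed the goal is an acceptable conservative option.

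Cost: wording only, with no new data collection. The bound is asymptotic and assumes that withdrawal is unrelated to event risk. With complete data its DSRC size is 5.21% at N = 231 and 5.27% at N = 242, against 3.60% and 3.67% for the exact test; this is the reason for the two-bound option. Power with constant hazard falls to about 84% at 20% withdrawal. If the rule is adopted, 12.1.1, 12.1.2, 12.2 and Appendix I should state the withdrawal rate on which the 85% power claim depends. No increase in N is asked for.
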